12.4.4 Handling of missing values not related to intercurrent event

Missing values will be handled using multiple imputation. In a first step the continuous LDL-C level will be imputed by m=100 imputations based on FAS. From the imputed continuous LDL-C level the primary endpoint will be derived against the set LDL-C target and analyzed with the methods described in regarding section. Results will be combined according to Rubin's rules on the log scale. The imputation model will impute missing values based on all observed data taking the intercurrent event strategy into account. The imputation model will include randomized treatment arm and the stratification factor.

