2.2.1 Subgroup of interest

Subgroup analysis for the following subgroups will be conducted for primary and the secondary endpoints:

- Age groups (18 – <65 years, 65 – < 75 and ≥ 75),
- Sex (male, female),
- CV risk category (very high risk, high risk).

Subgroup analyses will be conducted using the analyses as for primary and secondary endpoints which are included in the testing hierarchy including a subgroup and treatment-by-subgroup factor into the respective statistical analysis model (for negative binomial regression and logistic regression) and subgroup and treatment-by-subgroup, visit-by-subgroup and visit-by-treatment-by-subgroup factor (for MMRM). The estimates for the respective subgroup and corresponding 95% CI will be presented.

Subgroup analyses will only be performed if each subgroup includes more than 10 participants and additionally for binary outcomes if in at least one subgroup 10 events occurred. If there are still convergence issues for the subgroup analyses after considering all steps for in case of non-convergence (see [Section 5.5](#)), age categories may be combined.

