2.5.4 Handling of missing values not related to intercurrent event

Missing values will be imputed by multiple imputation. In a first step the continuous LDL-C level will be imputed by $m = 100$ imputations based on FAS. From the imputed continuous LDL-C level the binary response variable will be derived against the individual LDL-C target and analyzed with the methods described in the related section. Results will be combined according to Rubin's rules on the log scale. The imputation model will impute missing values based on all observed values taking into account strategy applied for the respective intercurrent event. The imputation model will include randomized treatment arm and CV risk category. Details are described in [Section 5.5.3](#).

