5.5.3 Multiple imputation

If not stated otherwise, imputation for primary and secondary analyses will be done by the following rules: For missing data, target day of the visit is considered to assess if missing is related or not related to intercurrent event. Absolute values are imputed corresponding endpoint variables are derived on imputed data.

Select data to fit the imputation model considering strategy applied for intercurrent events:

1. For primary endpoint all observed data will be included except for data collected after intercurrent events where composite strategy is applied, e.g. data collected after PCSK-9 inhibitors will be set to missing. Note, after death no data are collected, thus no need to take any action for while alive strategy. In case of occurrence of multiple intercurrent events e.g. double-blind treatment discontinuation and later PCSK-9 use, all data RDO data up to PCSK-9 inhibitor use will be used, others will be set to missing.
2. For secondary endpoints data all observed data will be included except for data collected after intercurrent events where hypothetical strategy is applied, these will be set to missing after intercurrent event. In case of occurrence of multiple intercurrent events e.g. double-blind treatment discontinuation and later PCSK-9 use, all RDO data up to

PCSK-9 inhibitor use will be used, others will be set to missing for LDL-C analyses where hypothetical strategy is applied for PCSK-9 inhibitor use.

3. Impute missing data using MAR (missing at random):

Select all participants, impute missing values at baseline and scheduled post-baseline visits, under assumption of missing at random (MAR), using the PROC MI procedure in SAS based on the fully conditional specification (FCS statement) method for 100 times and obtain 100 imputed datasets. Missing baseline values will be imputed using a model with treatment and CV risk category. Missing Day 30 values will be imputed using a model based on values of baseline, treatment and CV risk category. The same procedure will be repeated for subsequent visits.

This results in 100 imputed datasets.

For participants in the inclisiran treatment groups who discontinued double-blind treatment prematurely, set imputed values after discontinuation of double-blind treatment to missing, if not after occurrence of other intercurrent event such as PCSK-9 inhibitor, as these will be imputed using jump to reference (J2R) in step 4.

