4. For intercurrent event of double-blind treatment discontinuation, in case of missing RDO data and no occurrence of other intercurrent event such as PCSK-9 inhibitor impute missing values for participants in the inclisiran treatment groups using J2R.

Select all participants, impute missing values at scheduled post-baseline visits using the MI approach, under assumption of missing not at random (MNAR) that participants in inclisiran treatment groups will behave as participants treated with placebo, based on the fully conditional specification (FCS) method for 100 times and obtain 100 imputed datasets. Model will include same covariates as in step 1, except for treatment which is considered in the MNAR assumption.

This results in 100 imputed datasets.

5. Merge datasets from step 3 and step 4.

- a. For participants in inclisiran treatment groups discontinuing double-blind treatment prematurely take imputed values after discontinuation of double-blind treatment from step 4 if not after occurrence of other intercurrent event such as PCSK-9 inhibitor.
- b. For all other missing (including those for placebo participants) values take imputed values from step 3.

6. Derive endpoint variable for imputed values, e.g. change from baseline/response variable/percent change from baseline.

7. For each considered endpoint the specified analysis model will be applied on every of the 100 final multiply-imputed datasets where all missing values are filled (from MI or single imputation as defined by the respective strategy).

8. The results for the treatment effect from the 100 datasets will then be combined to obtain the statistical quantities of interest using Rubin's rule. Therefore, in SAS the PROC

MIANALYZE procedure is used and generates valid statistical inferences. If models failed to converge for a subset of imputations the remaining ones are used.

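### For the multiply imputed endpoints, the imputation model omits age group, sex and all treatment-by-subgroup terms that the planned subgroup models estimate, so supportive subgroup estimates are modestly distorted

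*SAP*

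**What the plan says.** **Subgroup models.** SAP 2.2.1 plans subgroup analyses by age group (three levels), sex and CV risk category. They reuse the analyses of the primary endpoint and of the secondary endpoints in the testing hierarchy, "including a subgroup and treatment-by-subgroup factor into the respective statistical analysis model". The MMRMs also get visit-by-subgroup and visit-by-treatment-by-subgroup terms. Estimates with 95% confidence intervals are presented; no interaction test is specified.

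**Imputation model.** SAP 2.5.4 states: "The imputation model will include randomized treatment arm and CV risk category". Protocol 12.4.4 agrees: "The imputation model will include randomized treatment arm and the stratification factor". Step 3 of SAP 5.5.3 gives the sequence: "Missing baseline values will be imputed using a model with treatment and CV risk category"; then "Missing Day 30 values will be imputed using a model based on values of baseline, treatment and CV risk category"; then "The same procedure will be repeated for subsequent visits". The Day 30 sentence applies directly to SF-BPI. Central-laboratory LDL-C has its first post-baseline analysis visit at Day 60 (SAP Table 2-1), so it falls under the last sentence.

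**Jump-to-reference step.** For step 4: "Model will include same covariates as in step 1, except for treatment which is considered in the MNAR assumption". The covariates are actually listed in step 3.

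**Link between the two.** SAP 2.5.2 takes the primary odds ratio from multiply imputed data. Step 7 of SAP 5.5.3 says that "the specified analysis model will be applied on every of the 100 final multiply-imputed datasets". The section's rules apply unless something else is stated, and nothing else is stated for subgroups.

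**The concern.** The subgroup models estimate terms that the imputation model does not contain. Age group and sex are absent from step 3, and CV risk enters only as a main effect. Given the earlier values, a missing inclisiran value is drawn with the average treatment effect, whatever the participant's subgroup.

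The tables that are meant to show whether the effect is consistent would then have some consistency built in. For LDL-C and SF-BPI, an MMRM fitted to the observed data would estimate subgroup-by-visit effects directly under the missing-at-random assumption that SAP 5.5.2.1 already makes. Imputing first, without those terms, overrides this.

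Part of the missingness is created by the plan. For mean LDL-C, values after PCSK9-targeting therapy or apheresis are set to missing and imputed. Protocol 3.4 ties PCSK9 antibody access to vascular disease with further risk factors or to HeFH, so these gaps may well differ by CV risk. That is an inference; the documents do not state it.

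**Working it through.** **No plan figure to reproduce.** The documents give no expected missing rate and no interaction size, and the response rates behind 880 per arm are redacted. The sizes below rest on assumed inputs.

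**1. Endpoints concerned.** Multiple imputation is used for the LDL-C target, mean percent change in LDL-C and the two SF-BPI scores (SAP 2.5.4 and 2.6.4). Muscle-related AEs are not imputed, and pain days are handled by an offset (SAP 2.6.4).

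**2. Approximate formula.** Let f be the fraction missing and k the share of the true interaction that imputed values still carry. Then

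estimated / true interaction = (1 - f) + f x k.

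- Day 60 also missing: k = 0, so the ratio is 1 - f. At f = 0.10 it is 0.90.
- Day 60 observed: k is about the visit correlation. With an assumed 0.6, the ratio is 1 - 0.4f. At f = 0.10 it is 0.96.

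**3. Simulation on the mg/dL scale.** From the documents: 1,760 participants, 1:1, and imputation of absolute values from arm, CV risk, baseline and earlier visit. Assumed: LDL-C reductions of 40% and 50% in two equal subgroups, mean baseline 95 mg/dL, residual SD 20 mg/dL, visit correlation 0.6. There were 200 trials per setting with 10 imputations each. Entries are the treatment-by-subgroup estimate after planned imputation divided by its full-data value.

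| Missing at Day 90 | Day 60 also missing: log OR | percent change | Day 60 observed: log OR | percent change |
|---|---|---|---|---|
| 5% | 0.955 | 0.954 | 0.977 | 0.983 |
| 10% | 0.893 | 0.900 | 0.966 | 0.962 |
| 20% | 0.811 | 0.808 | 0.930 | 0.934 |
| 30% | 0.679 | 0.696 | 0.862 | 0.882 |

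For example, at 10% with Day 60 also missing, 0.578 / 0.647 = 0.893. The table agrees with the formula to within about 0.02.

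**4. Other assumed inputs.** With a 30% subgroup, a log-odds interaction of about -1.07 and imputation of log LDL-C, attenuation was 4.8%, 11.0% and 14.4% at 5%, 10% and 15% missing if Day 60 was also missing. It was 2.1%, 4.4% and 7.1% if Day 60 was observed. A further run on the mg/dL scale gave about 5%, 10% and 16%, and 3%, 6% and 8%. Across the three sets, 5-10% missing gives about 5-11% without Day 60 and 2-6% with it.

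**5. Direction on percent change.** With no true percent interaction, but assumed mean baselines of 85 and 110 mg/dL and Day 60 also missing, the planned model gave an interaction of 1.25 points at 10% missing (full data 0.13) and 2.42 at 20% (full data 0.18). A common mg/dL shift is a smaller percentage of a higher baseline, so the model creates a difference here.

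**6. Size against precision.** With 1,760 participants and a 30% subgroup, the standard error of the log-odds interaction was about 0.24. For an interaction near -1.1 and 10% attenuation, 0.11 / 0.24 = 0.46 standard errors; simulated values at 5-10% missing were 0.11 to 0.45. For an interaction near -0.4 they were 0.05 to 0.19. Subgroup log odds ratios moved by at most about 0.06.

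**7. With the terms added.** Adding subgroup, treatment-by-subgroup, treatment-by-CV risk and treatment-by-baseline to the model of item 3 gave ratios of 0.98-1.00 (log OR) and 0.99-1.03 (percent change) at 5-30% missing. The interaction in item 5 fell to 0.07 at 10% and -0.27 at 20% (full data 0.08 and -0.14).

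**The case against.** The case for leaving the plan alone is fair on several counts. Protocol 12.4.7 labels the subgroup analyses supportive, and they are outside the testing hierarchy. Protocol 1.1 reports that inclisiran's efficacy was similar across subpopulations; where there is no real interaction there is little to attenuate. Retrieved drop-out data are used, and the Day 90 window for LDL-C runs from day 76 to day 120 and admits unscheduled visits, so missingness may be low. At 5-10% missing the bias is under about half a standard error.

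A reader might also infer more than the text supports:

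- **That all imputed values share one treatment effect.** They do not. An observed Day 60 value passes on its subgroup signal. Inclisiran discontinuers without retrieved data follow placebo by design, and users of PCSK9-targeting therapy or apheresis count as non-responders in the primary analysis. A common mg/dL shift also does not force a common odds ratio.
- **That subgroup differences always shrink toward zero.** Item 5 of the working shows otherwise for percent change.
- **That every subgroup table is affected.** Muscle-related AEs and pain days are not imputed.

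These arguments limit size and scope. They do not supply the missing terms: no section gives the subgroup runs an imputation model that matches their analysis model.

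**Conclusion.** The point holds as a minor one. For the four multiply imputed endpoints, the subgroup models estimate interactions that the step 3 model leaves out, and the subgroup estimates are distorted as a result. Under 5-10% missing and a sizeable true interaction, both assumed, attenuation on the log-odds scale is about 2-6% when Day 60 is observed and 5-11% when it is not. It grows with the missing fraction and is close to nil if effects are alike across subgroups. On percent change in LDL-C, the bias can run either way when baseline LDL-C differs between subgroups.

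It would be wrong to read this as a weakness of the primary result. The overall treatment effect, the confirmatory tests and type I error are unaffected.

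**What to change.** Leave the confirmatory imputation as it is. Add to SAP 2.2.1 and 5.5.3 that subgroup analyses of the LDL-C target, mean percent change in LDL-C and the two SF-BPI scores use a separate imputation run, with these changes:

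- Step 3 adds the subgroup factor and treatment-by-subgroup, treatment-by-CV risk and treatment-by-baseline terms at each visit. Because imputation goes visit by visit, this also covers the visit-by-treatment-by-subgroup terms of the MMRMs.
- Alternatively, step 3 imputes within arm with age group, sex and CV risk as covariates. This is not identical, since it also frees slopes and residual variance by arm, but it serves the same purpose.
- Step 4 adds the subgroup factor, and its cross-reference for covariates points to step 3.

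If one run serves all three factors, the extra terms per visit number 2 (age) + 1 (sex) + 2 + 1 + 1 (treatment by age, sex and CV risk) + 1 (treatment by baseline) = 8, against about 1,760 participants. A linear mg/dL model does not exactly contain a logistic or percent-change interaction, but the simulated recovery to within about 3% is adequate. A subgroup analysis of observed data would be a simple check.

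The cost is SAP wording, one additional set of imputations and slightly wider subgroup intervals; no new data are needed. If the database is already locked, report this as a labelled additional analysis.

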2.1.1.10 Reflexive LDL-C

The endpoints involving LDL-C will use a reflexive LDL-C approach. When both calculated and beta-quantified LDL-C are available, calculated LDL-C will be used unless triglycerides are greater than 400 mg/dL or calculated LDL-C is less than 40 mg/dL. When only calculated LDL-C or beta-quantified LDL-C is available but not both, the available one will be used. Only measurements from central lab will be used for the analyses.

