2.5.3 Handling of intercurrent events

The general strategy to account for different intercurrent events is summarized in [Table 2-2](#). Additional explanation is given in the following:

1. Discontinuation of investigational treatment:

Follow-up information after permanent discontinuation of investigational treatment, Retrieved Drop Out (RDO) data will be collected at regular study visits and will be included in the analysis, with treatments as assigned at randomization (treatment policy strategy). If no RDO data are collected missing data will be imputed using jump to reference as described in [Section 5.5.3](#).

2. Death:

For participants who die no subsequent LDL-C value can exist, therefore only pre-death data will be considered. For deceased participants the last value measured before death will be included into the analysis (while alive strategy).

3. Use of PCSK9 targeting non-study medication or lipid apheresis:

It could occur that participants are switched to PCSK9 targeting therapy after discontinuation of study medication or receive lipid apheresis. For the primary estimand participants who use PCSK9 targeting non-study medication or lipid apheresis will be considered as not achieving their LDL-C target (composite strategy).

4. COVID-19 pandemic impact on study:

For the primary estimand collected data will be included in the analysis. The treatment groups will be kept as assigned at randomization (treatment policy strategy). All observed data are used for the analyses, missing data are imputed as described in [Section 2.5.4](#).

Table 2-2 Account for different post randomization events for the primary endpoint reaching LDL-C target at day 90

Intercurrent event	Strategy
Permanent discontinuation of investigational treatment	Treatment policy strategy
Death	While alive strategy
Use of PCSK9- targeting non-study medication* or lipid apheresis	Composite strategy
COVID-19 pandemic impact on study	Treatment policy strategy
* evolocumab, alirocumab or commercially available inclisiran	

Change in background medication essentially concerns change in LLT during optimization. A change in background medication is therefore not considered as an intercurrent event because it is part of the treatments compared.

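### The jump-to-reference step in SAP 5.5.3, read naturally, carries out copy-reference imputation, and its covariates are not specified

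*SAP*

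**What the plan says.** For the primary estimand, SAP 2.5.3 handles stopping of blinded treatment by treatment policy and adds: "If no RDO data are collected missing data will be imputed using jump to reference". SAP 2.6.3 also names J2R for the secondary endpoints. SAP 5.5.3 step 4 carries it out, "under assumption of missing not at random (MNAR) that participants in inclisiran treatment groups will behave as participants treated with placebo", by fully conditional specification. Its covariates are given by a pointer: "Model will include same covariates as in step 1, except for treatment which is considered in the MNAR assumption".

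Step 1 only selects the data for the primary endpoint. The covariates are in step 3 (the missing-at-random step): "Missing Day 30 values will be imputed using a model based on values of baseline, treatment and CV risk category", followed by "The same procedure will be repeated for subsequent visits". No list is given for later visits. The section also states that values are imputed on the absolute scale, with changes and responses derived afterwards. Nowhere does it say that a participant's history is measured as a deviation from the mean of the participant's own arm. Copy-reference is not mentioned.

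**The concern.** J2R and copy-reference differ only in how on-treatment history is used. Under J2R, earlier values count as deviations from the inclisiran mean, so the expected value after stopping is the placebo mean. Under copy-reference, the placebo regression is applied to the raw on-inclisiran values. These lie below the placebo mean, so part of the gap is carried forward.

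Step 4 drops treatment from the model and centres nothing. If earlier post-baseline values are predictors, it is copy-reference. For LDL-C the departure goes one way: imputed values are lower than under J2R, in the inclisiran arm only. A reader would credit H01 and H02 with a more conservative rule than the one applied. SF-BPI (H05, H06) uses the same steps. No planned analysis would show the difference: Protocol 12.4.5 plans no sensitivity analysis, and the one in SAP 2.5.5 concerns risk-category protocol deviations.

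**Working it through.** The plan gives no figure to reproduce here, and the response rates behind the sample size are redacted.

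**From the documents.** For LDL-C, "Only measurements from central lab will be used for the analyses" (SAP 2.1.1.10), so the post-baseline analysis visits are Days 60, 90, 150, 330 and 360 (SAP Table 2-1). The planned size is 880 per arm.

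**Assumed, not in the documents.** Within-participant correlation ρ of 0.3–0.8, exchangeable or AR(1) across successive visits; equal SDs of 28 mg/dL; baseline 90 in both arms; placebo mean 68; constant inclisiran–placebo difference 25; target 55; 3% or 10% of the inclisiran arm affected (also 1% for Day 90).

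**1. Expected imputed value at visit t, given history H**

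- Copy-reference: μ_P,t + B(μ_I,H − μ_P,H), where B holds the placebo regression coefficients.
- J2R: μ_P,t, because deviations from the own-arm mean average zero.
- Share retained: (imputed mean − μ_P,t)/(μ_I,t − μ_P,t).

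**2. Share retained at the first missing visit**

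With k exchangeable history values, each coefficient is ρ/(1+(k−1)ρ), and the baseline gap is zero.

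| Last observed | Formula | ρ = 0.3 | ρ = 0.8 |
|---|---|---|---|
| Day 60, exchangeable | ρ/(1+ρ) | 0.3/1.3 = 23% | 0.8/1.8 = 44% |
| Day 90, exchangeable | 2ρ/(1+2ρ) | 0.6/1.6 = 38% | 1.6/2.6 = 62% |
| Either, AR(1) | ρ | 30% | 80% |

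Under AR(1) the share falls as ρ^j over successive visits. At ρ = 0.5 it is 50%, 25%, 12% and 6% after Day 60. With baseline and CV risk only, the history gap is zero, so the share is 0%.

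A simulation (880 per arm, 200 replicates) gave averages over the missing visits of 22–65% for the history-based model, −2% to +1% for joint-model J2R and about 0–2% for the baseline-only regression.

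**3. Mean LDL-C percent change (H02)**

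The difference is 25/90 = 27.8 points. If Day 60 is the last observed value, 4 of 5 visits are imputed. With 3% affected:

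- Exchangeable 0.3: 0.03 × 0.8 × 0.23 × 27.8 = 0.15 points.
- AR(1) 0.8: the mean share is (0.80 + 0.64 + 0.51 + 0.41)/4 = 0.59, and 0.03 × 0.8 × 0.59 × 27.8 = 0.39 points.

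The simulation gave 27.23 − 27.08 = 0.15 and 27.51 − 27.14 = 0.37. With 10% affected, the range is 0.5–1.3 points.

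**4. Day 90 responder rate (H01)**

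- J2R: P(LDL-C < 55) = Φ((55 − 68)/28) = 0.32.
- 23% retained: the mean is 68 − 0.23 × 25 = 62.2, which gives 0.40.
- 80% retained: the mean is 68 − 0.80 × 25 = 48, which gives 0.60.

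With 3% affected, the arm rate shifts by 3% × (0.40 − 0.32) to 3% × (0.60 − 0.32), about 0.2–0.8 points. With 1% it is 0.1–0.3, and with 10% it is 0.8–2.8.

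**The case against.** The strongest reply is that the SAP never says earlier post-baseline values are covariates. The only post-baseline list is baseline, treatment and CV risk. If that same list is reused at every visit, step 4 retains about 0% and the label is sound. This stands as far as it goes: the text does not settle the matter, so it cannot be stated as fact that copy-reference will be run. The natural reading still points that way. SAP 2.5.4 imputes from all observed values, step 3 builds up visit by visit, fully conditional specification conditions on the other variables, and only values imputed after discontinuation are reset before step 4. On the baseline-only reading, the missing-at-random step would also ignore an observed Day 60 value when imputing Day 90, which conflicts with SAP 2.5.4. Either way the text needs correction.

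The reach is narrow, and this stands in full. Step 4 applies only to inclisiran participants who stopped blinded treatment, have no retrieved data and have no PCSK9-targeting or apheresis event. For H01 only Day 60 can carry LDL-C history. The Day 90 sample is drawn before the second injection (Protocol 6.3.2), and participants who stop treatment are asked to keep attending visits (Protocol 9.1.1).

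Some carry-over may also be real, since SAP 2.4.1 credits each injection with 180 days of exposure. That could justify copy-reference as a choice. It does not justify calling it J2R under the stated assumption of placebo behaviour.

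A reader might infer that nearly all the benefit is kept late in follow-up. Suppose the gap shrinks through 35, 33, 28 and 22 mg/dL at Days 60, 90, 150 and 330. Exchangeable ρ of 0.4–0.7 then gives 96 × ρ/(1+3ρ)/22 = 79–99% retained at Day 330. A constant gap gives 3ρ/(1+3ρ) = 55–68%. The documents give neither the means nor the correlation, so they do not support the higher figures.

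**Conclusion.** The label and the model do not match on the natural reading, and the covariate pointer is wrong on any reading. For LDL-C the model so read is more favourable to inclisiran than the method named. For those imputed, the share of the difference kept at the first missing visit after Day 60 is roughly a quarter to four-fifths, depending on a correlation that the documents do not give. At trial level, with 3% affected, that is a few tenths of a point on H02, against a difference of about 27 points in the same model, and under one point on H01, where few participants should be affected. The SF-BPI effect cannot be sized, and its direction depends on an unknown pain difference.

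A reader might conclude that the primary result is materially biased. The documents do not support that: the number affected is unknown and probably small, and an immediate return to placebo levels is the SAP's assumption, not an established fact. The point is a specification error worth correcting, not a threat to the trial's conclusion.

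**What to change.** In SAP 5.5.3 step 4, replace the reference to step 1 with step 3, and list the covariates of steps 3 and 4 for each visit and endpoint. Then make step 4 deliver J2R in one of two ways:

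- Draw from the joint multivariate normal model with the own-arm mean before discontinuation and the placebo mean after it. Equivalently, take the placebo visit mean plus the placebo regression applied to the participant's deviations from the own-arm means. The placebo mean must be added back; centring alone is not enough.
- Use a placebo regression on baseline and CV risk only. This is simpler but ignores the participant's post-baseline history.

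If the sponsor prefers the history-based model, rename it copy-reference in SAP 2.5.3, 2.6.3 and 5.5.3, and add true J2R as a sensitivity analysis.

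The cost is SAP wording and some reprogramming of the imputation, with no new data. Moving to true J2R would make the inclisiran LDL-C estimate slightly less favourable.
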